## **20.0 Provisions to Protect the Privacy Interests of Participants**

### **20.1 Protecting Privacy:**

Interaction for all participants in our study will include an online screening survey, a vetting phone conversation, an email confirmation, followed by an online baseline survey and five follow-up surveys. In addition, all participants can contact the study at any time using our phone number and/or our study email. In all email and phone contact, we will maintain HIPPA compliant standards to ensure no privacy violations. (e.g., we will not describe the nature of the study in phone or email messages). In addition, data will be maintained in password protected files on a secure server.

Participants in the intervention group will also interact with study staff and other participants (in moderated forums). In addition to the safeguards listed above, participants will not be allowed to share personal information (such as full names) on forums, and will be informed of the risks of sharing personal information online.

### **18.2 Access to Participants:**

Our research team will not have access to medical records. However, in order to evaluate adherence, safety, and analyze the results of our study, we will collect information about PDE5-i use, prostate cancer treatment and side effects, and other health conditions. This information will be stored on password-protected, secured servers and will only be available to research staff who will use it for these purposes.

## **21.0 Compensation for Research-Related Injury**

21.1 Compensation for Research-Related Injury: N/A

21.2 Contract Language: N/A

## **22.0 Consent Process**

22.1 Consent Process (when consent will be obtained):

Following successful screening for eligibility, each potential participant will be sent an individual link for an online “chunked” consent page. (attached) Participants will view separate screens for each topic, specifically: 1) a description of our funding and researchers, 2) duration, compensation, and expected survey participation, 3) inclusion and exclusion criteria, 4) description of the intervention, 5) description of PDE5-I expectations and procedures 6) confidentiality policies, 7) participant risks, 8) benefits, and 9) contact information and next steps. At each page of the consent form, participants will click to confirm that they understand that page and wish to continue. On a final page, participants will click to confirm that they are eligible and wish to participate.

22.2 Waiver or Alteration of Consent Process (when consent will not be obtained, required information will not be disclosed, or the research involves deception):

N/A

22.3 Non-English Speaking Participants:

Because our study intervention includes English-language written and oral communication, non-English-speaking participants will not be eligible for this study.

22.4 Participants Who Are Not Yet Adults (infants, children, teenagers under 18 years of age):

N/A

22.5 Cognitively Impaired Adults, or adults with fluctuating or diminished capacity to consent:

Cognitively impaired adults will not be eligible for this study.

22.6 Adults Unable to Consent:

N/A

## **23.0 Setting**

23.1 Research Sites:

This study will be conducted entirely online. Participants will reside throughout the United States and will receive the intervention via a comprehensive website, mailed materials, and telephone conversations.

All team activities, including participant communication, intervention activities, and recruitment, will be based at the office facilities of the University of Minnesota Division of Epidemiology and Community Health.

## PROTOCOL TITLE: Restore: Gay Men and Prostate Cancer Aim III

Recruitment of participants will occur throughout the United States. Recruitment locations may include urologists, community groups in Minnesota and throughout the United States, and print and online advertisements. Recruiting urologists may provide printed materials to their GBM patients, with the approval of their local IRB boards.

23.2 International Research: N/A

23.3 Community Based Participatory Research: N/A

## 24.0 Multi-Site Research

N/A

## 25.0 Resources Available

25.1 Resources Available:

Our recruitment objectives are more than double the next largest study of GBM with PCa, so it is reasonable to doubt the feasibility of our goals. However, we're uniquely positioned to find participants because we have had the most success to date with recruitment. In addition, an NCI SPRINT grant provided us the structure to build relationships with referring partners nationwide and build the infrastructure needed to meet our ambitions.

ID: SPH-2018-26507

NCT03343093

November 13, 2023

Title: Restore: Improving Sexual Outcomes of Gay and Bisexual Prostate Cancer Survivors

Statistical Analysis Plan

Data Analysis Plan (NCT03343093)

The purpose of Hypothesis 3.1 is to test whether structured rehabilitation (intervention) will yield statistically significantly better QoL, sexual and urinary outcomes than routine care (control) over 24 months. The data to be analyzed will comprise of 9 measurement occasions (1 baseline measurement, 7 quarterly measurements and 1 final measurement). The primary outcomes are: (1) sexual function measured by overall SF and EPIC sexual function and bother scores, and (2) urinary function measured by overall UI and EPIC urinary function and bother scores. We will use a mixed-effects model for repeated measures data to investigate the difference in the overall improvement trajectory between the intervention group vs. the control group over 24 months of the study on the primary outcome variables. If we find the statistical evidence to support our hypothesis, we will run an additional secondary analysis where we will compare different facets/components of the intervention. That is, we will investigate the main effects, along with the interaction effects among the different components of the intervention. To test for Hypothesis 3.2, we will incorporate treatment type, demographics, and health status as moderator variables into the statistical framework of mixed-effects models. We will evaluate Hypothesis 3.3 to test whether the effects of intervention are greater in newly treated men (<2 years since prostate cancer treatment) vs. men 2+ years, post-treatment. We will analyze this hypothesis by using the grouping variable (early vs. long term) in the mixed-effects model to study the difference in the improvement trajectory of the two levels of this grouping variable. To evaluate Hypothesis 3.4 we will assess if the overall slope coefficient for the men 2+ years post-treatment obtained from the mixed-effects model is statistically significant. The analysis of Hypothesis 3.5 would include the dependent variable of Climacturia, measured by single items from the GSFS scale, and the intervention components of pelvic floor exercises and PDE5-I drugs are the predictors/independent variables. We will test if pelvic floor exercises and PDE5-I drugs can predict improvement in Climacturia over time by using a mixed-effects model.

Power Estimation. We expect 80% power to detect the statistically significantly differences between the intervention group and the control group. The power calculation was based on standardized effect size = 0.35, total number of observations per participant during the course of the study, $M = 9$, total number of participants, $N = 450$, assumed within-subject variability, $\sigma^2 = 0.50$, assumed between-subject variability, $\tau^2 = 0.20$ and a linear change over time.

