### 6.2 Study Procedures:

Following successful screening (see below), participants will review an online consent form which overview the study, study tasks, outlines risks and benefits, strategies to reduce risks, and risk-benefit analysis. After this, they participate in an initial telephone call from the project coordinator where they have the opportunity to ask any questions and have them answered, as well as verify information for cross-validation purposes. Then, if confirmed eligible and unique, they receive access to the baseline survey. Participants who complete the baseline survey will then be randomized, via a computer assignment, to a treatment or control group.

Participants in the control group will be notified by email. Thereafter, they will be contacted occasionally with survey links and reminders. As needed, additional casual communications will be used to increase retention.

Participants in the treatment group will be emailed immediately with a username and password to access the intervention. They will be mailed their welcome packet within one week.

Surveys will be conducted at baseline, and at 3, 6, 9, 12, 18, and 24 months follow-up. Surveys are attached.

Interaction for all participants in our study will include an online screening survey, a vetting phone conversation, an email confirmation, followed by an online baseline survey and five follow-up surveys. In addition, all participants can contact the study at any time using a 1-800 and/or our study email. In all email and phone contact, we will maintain HIPPA compliant standards to ensure no privacy violations. (e.g., we will not describe the nature of the study in phone or email messages). In addition, data will be maintained in password protected files on a secure server.

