**PROTOCOL TITLE: Restore: Gay Men and Prostate Cancer Aim III**

months. All participants will receive follow-up surveys at months 3, 6, 9, 12, 18, and 24 (attached).

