**9.0 Study Duration**

**9.1 Describe:**

The duration anticipated for an individual participant's participation in the study. The total duration of participation is 24 months. Follow-up surveys will occur for both treatment and control groups at baseline, 3, 6, 12, 18, and 24 months. For participants in the treatment group, PDE5-I drugs will be provided for 12 months, but the online intervention will continue for 24 months.

The duration anticipated to enroll all study participants. We expect enrollment to last 13 months from January 2019 through February 2020. The duration anticipated to complete all study procedures and data analysis. The study will take five years total, including 15 months of preparation, 37 months of recruitment and intervention, and eight months for analysis.

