## 12.0 Number of Participants

### 12.1 Number of Participants to be Consented:

We plan to recruit 450 participants: 150 participants who have undergone treatment in the past two years and 300 who have had at least two years since their PCa treatment.

We expect 80% power to detect the statistically significant differences between the intervention group and the control group. The power calculation was based on standardized effect size = 0.35, total number of observations per participant during the course of the study,  $M = 9$ , total number of participants,  $N = 450$ , assumed within-subject variability,  $\sigma^2 = 0.50$ , assumed between-subject variability,  $\tau^2 = 0.20$  and a linear change over time.

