### 17.3 Power Analysis:

We expect 80% power to detect the statistically significant differences between the intervention group and the control group. The power calculation was based on standardized effect size = 0.35, total number of observations per participant during the course of the study, M = 9, total number of participants, N = 450, assumed within-subject variability,  $\sigma^2 = 0.50$ , assumed between-subject variability,  $\tau^2 = 0.20$  and a linear change over time.

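### The SAP and all three power statements count 9 measurement occasions, but the protocol schedules 7 or 6, so the stated 80% power rests on surveys that are not planned

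*SAP*

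**What the plan says.** **Occasions in the SAP.** The Data Analysis Plan describes "9 measurement occasions (1 baseline measurement, 7 quarterly measurements and 1 final measurement"). Within 24 months this means months 0, 3, 6, 9, 12, 15, 18, 21 and 24.

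**Occasions in the power statements.** Protocol 12.1, Protocol 17.3 (Power Analysis) and the SAP's Power Estimation give the same inputs: effect 0.35, N = 450, within-subject variance 0.50, between-subject variance 0.20, linear change, and M = 9, defined as the "total number of observations per participant during the course of the study". The claim in 17.3 reads: "We expect 80% power to detect the statistically significant differences between the intervention group and the control group".

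**Occasions in the protocol.**
- 6.2: "Surveys will be conducted at baseline, and at 3, 6, 9, 12, 18, and 24 months follow-up". That is 7 occasions.
- 6.2, further down: "followed by an online baseline survey and five follow-up surveys". That is 6 occasions, against the section's own list of six follow-ups.
- 6.3: "All participants will receive follow-up surveys at months 3, 6, 9, 12, 18, and 24". With baseline, that is 7.
- 9.1: "Follow-up surveys will occur for both treatment and control groups at baseline, 3, 6, 12, 18, and 24 months". That is 6, with no month 9.
- 13.4 pays for the baseline survey and for months 3, 6, 12, 18 and 24. That is 6.
- 20.1 repeats the count of baseline plus five follow-ups. That is 6.

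**Sample size.** Section 12.1 states: "We plan to recruit 450 participants". This equals the N in the power calculation. Neither document gives a dropout rate or an inflation for loss.

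**The concern.** The primary analysis compares trajectories over 24 months, so the survey times define its data. As written, the SAP describes a data set that no version of the protocol schedule produces, and a reader cannot tell whether month 9 belongs in it.

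The same count enters the power calculation. With fewer surveys each man's slope is estimated less precisely, so 9 in place of 7 or 6 overstates the information, by an amount that depends on the model. The statement also leaves out alpha, the time unit, what the 0.35 is standardised by, and whether tau² is an intercept or a slope variance. The 80% can therefore be neither checked nor corrected from the documents alone. With N equal to the recruitment target, any room for loss over two years of online follow-up is at best implicit.

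**Working it through.** **Step 1. Count the occasions.**

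| Source | Count |
|---|---|
| SAP, Data Analysis Plan | 1 + 7 + 1 = 9 |
| Protocol 6.2 (list) and 6.3 | 1 + 6 = 7 |
| Protocol 9.1 and 13.4 (lists) | 1 + 5 = 6 |
| Protocol 6.2 (second statement) and 20.1 | 1 + 5 = 6 |

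The nine-occasion layout needs months 15 and 21, which no section schedules. This step needs no modelling assumption.

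**Step 2. Try to reproduce the stated 80%.**

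From the documents: N = 450, 1:1 allocation (Protocol 6.1), d = 0.35, σ² = 0.50, τ² = 0.20, linear change, M = 9. Protocol 17.3 (Data Analysis Plan) names random coefficient models, which makes a random-slope calculation a natural reading.

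Assumed, because not stated: two-sided alpha 0.05, τ² as the slope variance, d scaled by the slope SD, time in years, full retention.

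Formulas:
- SSt = sum of (t − mean t)²
- rel = τ² / (τ² + σ²/SSt)
- λ = (N·d²/4) × rel
- power = Φ(√λ − 1.96)
- N for 80% = 4 × 7.849 / (d² × rel), rounded up

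Here N·d²/4 = 450 × 0.1225 / 4 = 13.781.

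Nine surveys: SSt = 3.750, rel = 0.20 / (0.20 + 0.1333) = 0.600, λ = 8.269, √λ = 2.876, power = 0.820. With a t reference on 448 degrees of freedom it is 0.818. This is close to the stated 80%. It is a reconstruction, not the sponsor's calculation.

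**Step 3. Change only the survey times.**

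| Surveys (months) | SSt | rel | λ | Power | N for 80% |
|---|---|---|---|---|---|
| 9 (0, 3, …, 24) | 3.750 | 0.600 | 8.269 | 0.820 | 428 |
| 7 (0, 3, 6, 9, 12, 18, 24) | 2.982 | 0.544 | 7.497 | 0.782 | 472 |
| 6 (0, 3, 6, 12, 18, 24) | 2.969 | 0.543 | 7.481 | 0.781 | 473 |

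The t reference gives 0.818, 0.780 and 0.779. The loss is about 4 points. Whether month 9 exists hardly matters for power, because the 24-month span is unchanged.

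**Step 4. Compare with 450.** On this reconstruction nine surveys leave 450 − 428 = 22 men spare (22/450 = 4.9%). Seven surveys leave the plan 472 − 450 = 22 short, and six leave it 23 short, before any loss.

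**Step 5. Check how far this depends on the time unit.** With the same formula and time in quarters, SSt is 60.0, 47.7 and 47.5, and power is 0.953, 0.951 and 0.951. The change is then negligible. This version does not reproduce 80% at M = 9, so it is not a rival estimate of the cost. It shows only that the answer turns on inputs the documents leave out.

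**The case against.** The strongest reply is that the practical harm is small. A mixed model can be fitted to whatever surveys exist, so the analysis is not blocked. The closest reconstruction loses only about 4 points. Men who drop out still contribute the surveys they completed, and the 22 spare at nine surveys may have been meant as slack. M = 9 may also be a design-stage figure that was never updated. All of this is fair, and it limits the weight of the point. It does not make 9 the right count, it does not explain why the SAP describes the data to be analysed as nine occasions, and the documents nowhere call the slack an allowance.

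Two stronger readings are tempting but unsupported.
- A reader might infer that the trial is underpowered. The documents do not show this, because the inputs that would decide it are missing and at least one parameterisation leaves power almost unchanged.
- A reader might infer a loss of up to about 10 points, since a random-intercept model with the end-of-study effect scaled on τ goes from 0.623 to 0.527. That model gives 62% at nine surveys, so it cannot be the calculation behind the stated 80%, and its loss does not measure the cost of the error.

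**Conclusion.** The point holds as a discrepancy in the plan. Nine occasions are stated in the SAP and used in all three power statements, against seven or six in the protocol, which also disagrees with itself about month 9. This part is certain from the text.

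The effect on power is not certain. The best available estimate is 0.82 falling to 0.78, with the N for 80% rising from 428 to 472 or 473. It rests on the assumptions listed in the working and on full retention. A fall below 80% is possible but not proven. What is established is that the 80% uses an input that does not match the design, cannot be checked as stated, and carries no stated allowance for loss. This should be fixed, and the schedule contradiction is a better reason for that than the lost power.

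**What to change.** 1. Reconcile the survey schedule across Protocol 6.2, 6.3, 9.1, 13.4 and 20.1 and the SAP, and say whether month 9 exists.
2. In the SAP, replace the nine occasions with the actual survey times that enter the 24-month trajectory.
3. Restate the power, or the detectable effect, for those times. Give the sponsor's own alpha and sidedness, time unit, effect scale, definitions of σ² and τ², and an explicit assumption about loss.
4. If the M = 9 figure is kept, in the protocol or the SAP, label it as a design-stage assumption.

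The cost is wording in both documents and one restated figure, which may be slightly less favourable than 80%. No extra participants or surveys are needed. On the planned dates in Protocol 9.1 (enrolment to February 2020, then 24 months) collection would have ended about February 2022, before the SAP's date of November 2023. If those dates were kept, the sponsor already knows the survey times, and the restated figure documents precision and does not alter the design. The documents give planned dates only, so this should be confirmed.

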## 6.0 Procedures Involved

### 6.1 Study Design:

We will conduct a randomized controlled trial. Participants will be randomized 1:1 to receive either the online intervention or usual care. Treatment groups will be determined via permuted block randomization and will be stratified by relationship status and time since treatment (<2 years vs 2+years) with blocks of four.

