## PROTOCOL TITLE: Restore: Gay Men and Prostate Cancer Aim III

All analyses will be completed in STATA version 12.0. Comparisons between the intervention and control groups and the outcome measures (EPIC Urinary, Hormone, Sexual, and Bowel, as well as FACT-P and BSI-18 scores) will be evaluated using random coefficient modeling. Stratified analyses will be conducted by time since treatment (2+ years vs <2 years) and relationship status. Models may be adjusted for treatment time, relationship status, comorbidities and demographic variables.

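### The primary model does not say how the pre-randomisation baseline is handled; stating one common baseline mean for both arms would cost nothing and could sharpen the trajectory comparison

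*SAP*

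**What the plan says.** The SAP (Data Analysis Plan, Hypothesis 3.1) describes the data as nine occasions: "1 baseline measurement, 7 quarterly measurements and 1 final measurement". Baseline is therefore part of the analysed outcome. The model is described in these words: "We will use a mixed-effects model for repeated measures data to investigate the difference in the overall improvement trajectory". The target is the "difference in the overall improvement trajectory between the intervention group vs. the control group over 24 months of the study".

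Protocol section 17.3 (Data Analysis Plan) says that the outcomes "will be evaluated using random coefficient modeling". On covariates it adds: "Models may be adjusted for treatment time, relationship status, comorbidities and demographic variables". The baseline score of the outcome is not in that list, and the adjustment is optional.

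Protocol section 6.2 fixes the order of events: "Participants who complete the baseline survey will then be randomized, via a computer assignment, to a treatment or control group". Section 6.1 gives a 1:1 allocation.

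Neither document writes out the fixed effects. It is not stated whether each arm has its own intercept, whether the arms share one, or whether baseline enters as a covariate.

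**The concern.** Because baseline is measured before randomisation, the true arm means at time 0 are equal by design. The common default for a random-coefficient model is arm, time and arm-by-time, which gives each arm its own intercept. That model spends information on estimating a difference known to be zero.

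The estimated slope and intercept are correlated. The arm-by-time estimate therefore moves with whatever chance difference the arms show at baseline, and its variance can be larger than it need be. The same applies to every outcome compared between randomised arms with this model.

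Leaving the choice open also means that several primary analyses, with different estimates and P values, fit the text equally well.

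**Working it through.** **Inputs from the documents.** N = 450, M = 9, standardised effect 0.35, within-subject variance 0.50, between-subject variance 0.20, linear change (SAP, Power Estimation; repeated in Protocol sections 12.1 and 17.3). Visits at 0, 3, 6, 9, 12, 18 and 24 months (Protocol section 6.2).

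**Assumptions, not in the documents.** Two-sided alpha 0.05; time in years; 0.20 read as slope variance; intercept variance 0.2 to 1.0; intercept-slope correlation -0.3 to +0.3; no dropout; normal approximation.

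**Step 1: reproduce the stated power.** Sampling variance of one man's fitted slope with nine quarterly visits (f = 4 per year):

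V = 12 × 0.50 × 4² / (8 × 9 × 10) = 0.1333

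Reliability = 0.20 / (0.20 + 0.1333) = 0.60. Noncentrality = 450 × 0.60 × 0.35² / 4 = 8.27, square root 2.876, so power = Φ(2.876 - 1.960) = 0.820 (0.818 with the noncentral t). This is close to the stated 80% and uses no baseline constraint. Two other readings do not reproduce it: taking one visit as the time unit gives 0.953, and a random-intercept comparison of averages over nine occasions gives more than 0.999.

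With the seven visits of section 6.2, mean time is 6/7 = 0.857 and the sum of squares about it is 8.125 - 36/7 = 2.982. Then V = 0.50 / 2.982 = 0.1677, reliability 0.544, noncentrality 7.50 and power 0.782.

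**Step 2: effect of a common baseline mean.** The covariance of one man's fitted (intercept, slope) is D + σ²(X'X)⁻¹, where D is the random-effects covariance. Fixing the arm difference in intercept at zero multiplies the slope-difference variance by 1 - r², where r is the correlation of those two estimates. It can never raise the variance.

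Seven visits, intercept variance 0.2, correlation 0:

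- intercept variance of the estimates: 0.2 + 0.50 × (1/7 + 0.857²/2.982) = 0.395
- slope variance of the estimates: 0.20 + 0.1677 = 0.368
- covariance: -0.50 × 0.857 / 2.982 = -0.144
- r² = 0.144² / (0.395 × 0.368) = 0.142
- new noncentrality 7.50 / 0.858 = 8.74, power 0.84

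Same calculation over the assumed range (variance ratio is constrained over unconstrained):

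| Intercept variance | Correlation | Ratio, 7 visits | Power from 0.782 to | Ratio, 9 visits | Power from 0.820 to |
|---|---|---|---|---|---|
| 0.2 | -0.3 | 0.714 | 0.900 | 0.712 | 0.926 |
| 0.2 | 0 | 0.858 | 0.841 | 0.863 | 0.872 |
| 0.2 | +0.3 | 0.952 | 0.801 | 0.959 | 0.836 |
| 0.5 | -0.3 | 0.777 | 0.874 | 0.773 | 0.905 |
| 0.5 | 0 | 0.919 | 0.815 | 0.923 | 0.849 |
| 0.5 | +0.3 | 0.991 | 0.786 | 0.994 | 0.823 |
| 1.0 | -0.3 | 0.824 | 0.855 | 0.819 | 0.888 |
| 1.0 | 0 | 0.953 | 0.801 | 0.955 | 0.837 |
| 1.0 | +0.3 | 1.000 | 0.782 | 1.000 | 0.820 |

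With seven visits and zero correlation, the gain equals 450 × r²/(1 - r²) = 75, 40 or 22 extra men for intercept variance 0.2, 0.5 or 1.0.

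**Step 3: dependence on the chance baseline difference** (nine visits, arm-specific intercepts, intercept variance 0.2, correlation 0). The SD of the observed baseline difference is √[(0.2 + 0.50) × 4/450] = 0.079. The regression of the estimated slope difference on it is -0.1333 / 0.70 = -0.190. A 1-SD imbalance shifts the slope difference by -0.190 × 0.079 = -0.015. The design effect is 0.35 × √0.20 = 0.157, so the shift is about 10% of it. Over the assumed range it runs from about 0% to 14%. With a common baseline mean it is zero.

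**The case against.** The strongest reply is that no wrong model has been shown. A model with time and arm-by-time and one shared intercept fits the SAP and Protocol wording as well as the usual three-term model does. That stands: the point is about something left unspecified.

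A reader might also draw four stronger conclusions. The documents do not support them.

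- *That a baseline difference in level carries through into the result, or that the analysis is biased.* With arm-specific intercepts, the intercept absorbs the level difference. What remains is the conditional dependence in step 3. Averaged over randomisations there is no bias, and type I error is not inflated.
- *That the arm starting lower will always seem to improve faster.* The direction depends on the intercept-slope correlation, which is not given. At intercept variance 1.0 the dependence vanishes near a correlation of +0.3 and reverses beyond it.
- *That the 80% power claim fails here.* Step 1 reaches 82% with M = 9 and no constraint. The 78% arises because section 6.2 lists seven surveys rather than nine, which is a separate inconsistency.
- *That arm differences at single visits are affected.* The written Hypothesis 3.1 compares trajectories, and no single-visit arm contrast is specified.

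It is also fair to say that the size of the gain rests on variance components chosen for this check and can be close to nil. What survives is that the gain is never negative and nothing is paid for it.

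**Conclusion.** The point holds as a free improvement to an under-specified model. As written, the plan treats a pre-randomisation baseline as an outcome and states neither an adjustment for it nor a common baseline mean. An unconstrained slope comparison would be valid, but possibly less precise than the same data allow.

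The variance of the arm-by-time effect would fall by about 0 to 29%, and by about 5 to 14% if intercept and slope are uncorrelated. These figures require 0.20 to be the slope variance, the reading that reproduces the stated power, and an intercept variance and correlation within the assumed ranges. If 0.20 were instead a random-intercept variance with no random slope, the reduction with nine visits would be 34%, but a random-intercept comparison of averages does not reproduce 80% power.

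**What to change.** Write out the Hypothesis 3.1 model in the SAP: baseline stays in the outcome vector; the fixed effects are time and arm-by-time with one common baseline mean (no arm main effect at time 0); random intercept and slope. Use the same constraint for the other comparisons between randomised arms. In the moderator and time-since-treatment models (Hypotheses 3.2 and 3.3), constrain the arms to be equal within each moderator level and let the levels keep their own baseline means, because those were not randomised.

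The cost is one line of SAP wording and the matching model code. No data or men are lost, since only men who complete the baseline survey are randomised.

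Including the two randomisation stratification factors (relationship status and time since treatment) is a separate improvement and contributes none of the gain quoted above.
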